#### **4.1.3 Presentation of results**

All analyses will use SAS® version 9.3 or higher.

If not stated otherwise, summary tables will be presented according to the data used:

- Tables using combined data from feeder studies (i.e., studies D3461C00004 and D3461C00005) and LTE study will be presented by combined treatment group as defined in Section 2.1.6 (randomised anifrolumab 300 mg, randomised placebo, placebo feeder + placebo LTE, and all anifrolumab). For some tables, if mentioned explicitly, the additional supportive treatment groups placebo feeder + anifrolumab

300 mg LTE, and anifrolumab 150 mg feeder + anifrolumab 300 mg LTE will also be presented.

- Tables using data of the LTE study only will be presented by LTE treatment group as defined in Section 2.1.6 (randomised anifrolumab 300 mg, placebo feeder + placebo LTE, placebo feeder + anifrolumab 300 mg LTE, and anifrolumab 150 mg feeder + anifrolumab 300 mg LTE,)

For by-visit presentations, only baseline, Week 24, and Week 52 will be presented for the Phase 3 feeder studies. If not stated otherwise, results of a specific treatment group and visit will be suppressed if the summary is based on data of less than 25 subjects. For all other presentations, all available data for each analysis set will be used in the analyses. Data collected during the LTE study (including derived variables and baseline from the Phase 3 feeder studies) will be presented in listings sorted by LTE treatment group and subject number. A separate document will be produced containing the template table, listing, and figure shells.

Unless otherwise noted, categorical data will be presented using counts and percentages with the denominator for percentages being the number of subjects in the analysis set by treatment group. Percentages will be rounded to 1 decimal place; except 100% which will be displayed without any decimal places. Percentages will not be displayed for zero counts.

Unless otherwise noted, continuous variables will be summarised using the number of observations (n), mean, standard deviation (SD), median, minimum, and maximum. The minimum and maximum values will be displayed to the same level of precision as the raw data; the mean, median, and quartiles to a further decimal place; and the SD to 2 additional decimal places. CV% [REDACTED] will be presented with 1 decimal place.

Due to the limitation of the Rothman and Greenland method for 0 outcomes, the exact Poisson confidence intervals for event rates will be calculated.

$$\text{Lower bound} = e^{\left[ \ln(\text{rate}) - Z_{1-\frac{\alpha}{2}} \frac{1}{\sqrt{\text{number of events}}} \right]}$$

$$\text{Upper bound} = e^{\left[ \ln(\text{rate}) + Z_{1-\frac{\alpha}{2}} \frac{1}{\sqrt{\text{number of events}}} \right]}$$

The corresponding confidence intervals to those used in the sample size estimation, but using the exact Poisson are as follows:

Assuming follow-up times of approximately 893, 517, and 1343 subject years for the “Randomised Anifrolumab 300 mg,” “Randomised Placebo,” and “All Anifrolumab” treatment groups are expected. Given this exposure, the 95% CIs for an AESI for which the observed incidence rate is 10 events in 1000 subject years will be 4.56 to 19.03 for “Randomised Anifrolumab 300 mg,” and 3.32 to 23.03 for “Randomised Placebo.” For an AESI for which the observed incidence rate is 1 event in 1000 subject years, the 95% CI will be 0.0173 to 6.03 for “Randomised Anifrolumab

300 mg,” arm; 0.001 to 9.10 in the “Randomised Placebo,” arm ; and 0.056 to 4.58 in the “All Anifrolumab” arm.

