If an AE has a missing onset date, then unless the stop date of the AE indicates otherwise, it will be assigned to the “Year 1” time interval. Similarly, if an AE has a partial onset date, then unless the partial onset date or the stop date indicates otherwise, it will be assigned to the earliest time interval given the available date information. If the missing or partial start date does not allow an assignment of the event as during the Phase 3 feeder studies or the LTE study, the AE will be assigned to “Year 1” if documented in one of the Phase 3 feeder studies or to “Year 2” if documented in the LTE.

The event rate per 100 subject years is defined as the number of subjects with an event divided by the sum of exposure time in days in the respective time period for all subjects in the analysis set multiplied by 365.25 days/year multiplied by 100. The exposure in a time period for each subject will be calculated as end of period – start of period + 1 (e.g., as the earlier of either (date of last dose of investigational product + 84 days, or date of study discontinuation) - date of first dose of investigational product + 1 day for the summary of all AEs during treatment and follow-up; for AEs during treatment, the same definition will apply, with the exception of last dose of investigational product + 28 days will be used). For analyses based on LTE data only (e.g. AE rates for subjects switching from Placebo to 300 mg anifrolumab in the “All Anifrolumab” treatment group), the first administration of investigational product during the LTE will be considered as the start of the overall period. For analyses based on feeder study data only (e.g. AE rates for subjects switching from Placebo to 300 mg anifrolumab in the “All Randomised Placebo” treatment group), the end of the overall period will be defined as the first administration of investigational product in the LTE -1 day. If a subject discontinued during a period or had the last follow-up visit earlier than expected, the date of study discontinuation/end of study will be used as end of the respective period.

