### **4.2.1 Analysis of the primary variables (safety variables)**

If not stated otherwise, safety variables will be summarised by combined treatment group for the full analysis set.

The primary assessment will be the comparison between the treatment groups “Randomised Anifrolumab 300 mg” and “Randomised Placebo”. The “All Anifrolumab” treatment group will be used to assess rare events.

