The event rate per 100 subject years including 95% CIs will be summarised for the following categories. Summaries of AESIs will be presented by AESI category (non-opportunistic serious infections, opportunistic infections, anaphylaxis, malignancy, herpes zoster, tuberculosis, influenza, vasculitis [non SLE], and major acute cardiovascular events) and preferred term. Summaries for SAEs will be presented by MedDRA system organ class and preferred term.

- Any AESI
- Any AESI by time interval for the first onset of event – alternative event rates
- Any AE leading to discontinuation of IP by time interval for the first onset of event – alternative event rates (combined feeder & LTE study, by preferred term)
- Any AESI – alternative event rates
- Any SAE (including events with outcome = death) (during treatment and during follow-up separately. No event rate for during follow-up will be presented)
- Any SAE (including events with outcome = death) by time interval for the first onset of event – alternative event rates

The event rate per 100 subject years will be summarised by MedDRA system organ class and preferred term for the following AE categories.

- Any AE (during treatment and during follow-up separately. No event rate for during follow-up will be presented)
- Any AE by descending preferred term (during treatment, and during the LTE treatment)
- Any AE with outcome = death
- Any SAE by descending preferred term (including events with outcome = death) (during treatment, and during the LTE treatment)
- Any AE leading to discontinuation of investigational product
- Any AE by relationship to investigational product (yes, no) (multiple occurrences of an AE in 1 subjects will only be counted once as related if at least one AE is related and as not related if all occurrences are not related)
- Any AE by maximum intensity (mild, moderate, severe) (i.e., multiple occurrences of an AE in 1 subjects will only be counted once with the maximum intensity in this AE)
- Any other significant AE

The alternative event rate per 100 subject years will be summarised by MedDRA preferred term for the following AE categories.

- Any COVID-19 related AE (for the LTE Study only, only subjects remaining in the study on 11-Mar-2020 will be included)
- Any SAE prior to the COVID-19 pandemic (for the LTE Study only)
- Any SAE during the COVID-19 pandemic (for the LTE Study only, only subjects remaining in the study on 11-Mar-2020 will be included)

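### SAP 4.1.3 names exact Poisson intervals because of zero-event cells, but the formula it prints is a log-normal interval that is undefined at zero events and reproduces none of the five intervals quoted beneath it

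*SAP*

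**What the plan says.** SAP 4.1.3 gives the interval method for event rates and the reason for it: "Due to the limitation of the Rothman and Greenland method for 0 outcomes, the exact Poisson confidence intervals for event rates will be calculated". Two equations follow directly, one for each bound: exp[ln(rate) − Z/√(number of events)] and the same with a plus sign. They carry no other label. The SAP then writes "The corresponding confidence intervals to those used in the sample size estimation, but using the exact Poisson are as follows" and, at 893, 517 and 1343 subject-years, lists five 95% intervals; the first "will be 4.56 to 19.03 for" Randomised Anifrolumab 300 mg.

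These intervals feed the primary outcome. SAP 4.2.1.1 says "The event rate per 100 subject years including 95% CIs will be summarised for the following categories". That list covers AESIs by category and preferred term and SAEs by system organ class and preferred term, some of them also by time interval. SAP 4.2.1 adds that the All Anifrolumab "treatment group will be used to assess rare events".

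SAP 1.3 and protocol 8.2 give planning intervals for the same exposures and label them Rothman-Greenland. Those are not in dispute.

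**The concern.** The named method, the formula and the worked figures should describe one calculation. The formula does not match the other two. It needs ln(0) and 1/√0 when no event is seen, so it fails in the situation that prompted the move to exact limits.

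No formal comparison is planned, so the point estimates and intervals by group are the inferential output for AESIs and SAEs. With tabulation down to preferred term, and in places by year, sparse cells are to be expected, although the documents give no event counts. In those cells a program written from the printed formula would return no interval at 0 events, and at 1 or 2 events limits well away from those of the named method. For the All Anifrolumab group, which is assigned to rare events, the upper limit is the useful result.

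**Working it through.** **Inputs (SAP 4.1.3).** T = 893 (Randomised Anifrolumab 300 mg), 517 (Randomised Placebo) and 1343 (All Anifrolumab) subject-years (SY); observed rates of 10 and 1 per 1000 SY; two-sided 95%, Z = 1.96. The event count is d = rate × T, kept fractional: 8.93, 5.17, 0.893, 0.517 and 1.343.

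**Formulas.**
- Exact Poisson: lower = χ²(0.025; 2d)/(2T), upper = χ²(0.975; 2d+2)/(2T).
- Printed in the SAP: rate × exp(∓1.96/√d).

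**Step 1: reproduce the plan's figures.** For 10 per 1000 at 893 SY, the exact limits are χ²(0.025; 17.86)/1786 = 8.137/1786 = 4.556 per 1000 and χ²(0.975; 19.86)/1786 = 33.986/1786 = 19.029 per 1000. These match the quoted 4.56 and 19.03. The printed formula gives 1.96/√8.93 = 0.656 and exp(0.656) = 1.927, hence 10/1.927 = 5.19 and 10 × 1.927 = 19.27.

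All five scenarios, per 1000 SY:

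| Rate, T | d | Quoted in SAP 4.1.3 | Exact, recomputed | Printed formula |
|---|---|---|---|---|
| 10, 893 SY | 8.93 | 4.56–19.03 | 4.556–19.029 | 5.19–19.27 |
| 10, 517 SY | 5.17 | 3.32–23.03 | 3.325–23.031 | 4.22–23.68 |
| 1, 893 SY | 0.893 | 0.0173–6.03 | 0.0173–6.030 | 0.126–7.96 |
| 1, 517 SY | 0.517 | 0.001–9.10 | 0.0012–9.102 | 0.0655–15.27 |
| 1, 1343 SY | 1.343 | 0.056–4.58 | 0.0564–4.583 | 0.184–5.43 |

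The exact formula recovers all five intervals; the printed formula recovers none. Rounding d to an integer, or using 90% limits, does not make it match.

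**Step 2: compare with the planning intervals.** SAP 1.3 gives, in the same order, 5.21–19.21, 4.24–23.57, 0.13–7.95, 0.07–15.25 and 0.18–5.42, labelled Rothman-Greenland. The printed formula lies close to these. It is therefore close to the method that the sentence above it sets aside.

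**Step 3: zero events.** The exact interval is 0 to −ln(0.025)/T = 3.689/T. That gives upper limits of 4.13 (893 SY), 7.14 (517 SY) and 2.75 (1343 SY) per 1000 SY. The printed formula has no value.

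**Step 4: small counts.** The ratio of printed to exact limits depends only on the count:

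| Events | Example T | Printed | Exact | Lower ratio | Upper ratio |
|---|---|---|---|---|---|
| 1 | 517 SY | 0.27–13.73 | 0.05–10.78 | 5.6 | 1.27 |
| 1 | 1343 SY | 0.10–5.29 | 0.02–4.15 | 5.6 | 1.27 |
| 2 | 1343 SY | 0.372–5.95 | 0.180–5.38 | 2.1 | 1.11 |
| 5 | 517 SY | 4.03–23.24 | 3.14–22.57 | 1.28 | 1.03 |
| 9 | 893 SY | 5.24–19.37 | 4.61–19.13 | 1.14 | 1.01 |

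Both printed limits are too high relative to the exact ones.

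**Step 5: how often zero might occur.** Assume Poisson counts and a true rate equal to the plan's illustrative 1 per 1000 SY. Then P(0 events) = exp(−T/1000) = 0.409 at 893 SY, 0.596 at 517 SY and 0.261 at 1343 SY.

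**The case against.** The strongest reply is that the SAP resolves the matter itself. It names the method in words, gives the reason, and prints five correct intervals that a programmer can use as check values. Anyone coding the equation would get no result at zero events and would fail all five checks. The equations may simply be the Rothman-Greenland formula, shown as the method with the limitation and left unlabelled. Step 2 makes that plausible but does not prove it: replacing 1/√d by √((1−rate)/d), with the rate per subject-year, comes closer still to the SAP 1.3 figures. The log-normal interval is also a recognised approximation, its upper limit is within 3% of the exact one from 5 events upward, and no decision rule or sample size depends on it.

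Most of this is fair. A careful reader can recover the intent, and the printed limits are wrong only relative to the method the SAP names. It does not remove the contradiction. The equations follow directly on the exact Poisson sentence with no other label, and neither document prints an exact formula. If they were meant as Rothman-Greenland, they still need that label and the exact formula is still missing. The lower limit remains 28% too high at 5 events.

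One further point is separate. Protocol 8.5.1 describes incidence as events over person-time, whereas SAP 3.1.1 counts subjects with an event. Correcting the interval formula does not settle that difference.

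**Conclusion.** The concern holds. The formula in SAP 4.1.3 contradicts both the method named in the same section and all five intervals worked there, and it cannot be evaluated at zero events. The quoted intervals are right; the displayed formula is the error. The effect is largest in sparse cells: no interval at 0 events, and at 1 event an upper limit 27% too high with a lower limit 5.6 times the exact one. By 9 events the upper limit differs by about 1%.

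The comparison of formulas rests only on the SAP's own exposures, rates and confidence level. The zero-event probabilities also assume Poisson counts and a true rate of 1 per 1000 subject-years, which the plan uses as an illustration and not as a forecast for any AESI. This should be fixed because the intervals describe the primary outcome, but it changes no design decision.

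**What to change.** In SAP 4.1.3, replace the two equations with the exact limits:

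- lower = χ²(α/2; 2d)/(2T), set to 0 when d = 0;
- upper = χ²(1−α/2; 2d+2)/(2T);
- multiply by 100 for rates per 100 subject-years.

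State that d is the numerator of the rate being reported, which SAP 3.1.1 defines as follows: "The event rate per 100 subject years is defined as the number of subjects with an event divided by the sum of exposure time". State that T is the matching denominator: summed exposure time for the event rate, and summed time at risk for the alternative event rate. If the sponsor wishes to keep the present equations for reference, label them as the method being replaced.

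Keep the five quoted intervals; they then serve as check values for the program. The cost is one formula and a sentence of definition in the SAP. The named method does not change and no protocol amendment is needed.

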#### **4.1.4 Missing Data**

For data captured in the Phase 3 feeder studies the same imputation of missing values using LOCF will be done as in the respective feeder study. No LOCF will be done for data captured in the LTE.

For data captured in the Phase 3 feeder studies the effect of missing items on a score will be handled in the same way as in the respective feeder study. For data captured in the LTE, unless otherwise defined, scores that are derived from summing up items will be considered missing if any of the items are missing.

[REDACTED]

Missing safety data will generally not be imputed. However, safety assessment values of the form of <x (i.e., below the lower limit of quantification (LLOQ)) or >x (i.e., above the upper limit of quantification) will be imputed as x in the calculation of summary statistics but displayed as <x or >x in the listings.

Anifrolumab serum concentrations reported as below the LLOQ will be imputed with LLOQ/2 for analysis. [REDACTED]

Details about imputation of partial or missing dates [REDACTED]

## **4.2 Analysis methods**

Where applicable, the analyses will include data from randomisation in the Phase 3 feeder studies until the end of the LTE study, regardless of whether study treatment was prematurely discontinued or delayed, and/or irrespective of protocol adherence.

### **4.2.1 Analysis of the primary variables (safety variables)**

If not stated otherwise, safety variables will be summarised by combined treatment group for the full analysis set.

The primary assessment will be the comparison between the treatment groups “Randomised Anifrolumab 300 mg” and “Randomised Placebo”. The “All Anifrolumab” treatment group will be used to assess rare events.

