## 1.2 Study design

This is a Phase 3, multicentre, multinational, randomised, double-blind, placebo-controlled extension study characterising the long-term safety and tolerability of an IV treatment regimen of anifrolumab (300 mg) versus placebo in subjects with moderately to severely active systemic lupus erythematosus (SLE) who completed a Phase 3 study (D3461C00004 or D3461C00005) through the 52-week double-blind treatment period.

Approximately 575 subjects from Studies D3461C00004 or D3461C00005 (also referred to as the feeder studies) who were previously treated with anifrolumab (150 or 300 mg) or placebo for 52 weeks while receiving standard of care (SOC) treatment and who are willing to continue treatment may participate in the long-term extension (LTE) study if all eligibility criteria are met. Subjects will receive either a fixed IV dose of 300 mg anifrolumab every 4 weeks (Q4W) for up to 39 doses (LTE Week 0 to LTE Week 152) or placebo. Investigational product (IP) will be administered as an IV infusion via an infusion pump over a minimum of 30 minutes, Q4W.

In order to ensure that subjects with active SLE who enter the LTE will have adequate treatment of their disease in this 3-year blinded, placebo-controlled extension study, Investigators will be allowed to change the background SOC treatment for SLE during the course of the study. This LTE protocol allows for adding a new oral immunosuppressant or changing background immunosuppressants, as well as for flexible oral corticosteroids (OCS) use, so that subjects may achieve adequate control of their disease on study. However, it is recommended that subjects receive the lowest possible corticosteroid dose.

In the LTE study, treatment assignment will follow an Interactive Voice/Web Response System (IXRS) algorithm as follows:

- Subjects previously treated with anifrolumab 300 mg IV will stay on blinded treatment
- Subjects previously treated with anifrolumab 150 mg will switch to blinded anifrolumab 300 mg
- Subjects previously randomised to placebo will be re-randomised 1:1 to blinded anifrolumab 300 mg or placebo

Therefore, in the LTE study subjects will receive double-blind treatment with either anifrolumab 300 mg or placebo in an approximate ratio of 4:1.

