Although the study will initially be completely double-blind (ie, blind for subjects, Investigators/site staff, and Sponsor/designated clinical research organisation [CRO]), at the conclusion of the Phase 3 Studies D3461C00004 or D3461C00005 treatment allocation for all subjects who were previously on active treatment will become known to the Sponsor staff and/or designated CRO. The blind will be maintained for the Investigator and investigational site staff, for select roles at the CRO, and for the subjects. Further details are described in a separate unblinding plan.

In general, the first dose of study drug in the LTE study (LTE Day 1/Visit 1/Week 0) should occur on the same day as the final study visit of the prior study (ie, Week 52); however, special circumstances may warrant a delay in subject randomisation of up to 30 days following the final visit of the prior study (ie, Week 52). Administration of study drug in the LTE study should not occur until all LTE Day 1/Visit 1/Week 0 evaluations are completed.

This LTE study includes:

- **Treatment Period:** A 156-week treatment period with investigational product administered Q4W from LTE Week 0 to LTE Week 152 for a total of 39 doses. During the treatment period, visits will be scheduled for each Q4W administration.
- **At LTE Week 156 (or after the last dose of investigational product)** subjects will continue in the study for another 8 weeks to complete a 12-week safety follow up after the last dose of investigational product (last dose of investigational product will be given at LTE Week 152).

The total study duration will be up to approximately 164 weeks (including a 12-week Follow up Period after administration of the final dose).

Once subjects have completed Studies D3461C00004 or D3461C00005 (through Week 52), signed the informed consent form, and met all study eligibility criteria, they may be included in the LTE study.

In the event a site has not obtained the required approval (e.g., regulatory authority, local ethics committee) by the time a subject is eligible to be randomised in the LTE study, the site may be allowed the time to obtain the approval(s).

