### **1.3 Number of subjects**

No formal comparisons are planned in this study; point estimates and confidence intervals (CIs) will be presented for each treatment group separately. The sample size is not based on statistical considerations, but is defined as all subjects who completed the treatment period in

the Phase 3 feeder Studies D3461C00004 or D3461C00005 (through Week 52) and met all study eligibility criteria. Assuming annual dropout rates of 30%, 30%, and 20% following placebo, anifrolumab 150 mg, and anifrolumab 300 mg, and that 90% of the subjects completing studies D3461C00004 or D3461C00005 enter the LTE, follow-up times of approximately 893, 517, and 1343 subject years for the “Randomised Anifrolumab 300 mg,” “Randomised Placebo,” and “All Anifrolumab” treatment groups are expected. Given this exposure, the 95% CIs for an AESI for which the observed incidence rate is 10 events in 1000 subject years will be 5.21 to 19.21 for “Randomised Anifrolumab 300 mg,” and 4.24 to 23.57 for “Randomised Placebo.” For an AESI for which the observed incidence rate is 1 event in 1000 subject years, the 95% CI will be 0.18 to 5.42 for “All Anifrolumab” (0.13 to 7.95 for “Randomised Anifrolumab 300 mg”), and 0.07 to 15.25 for “Randomised Placebo,” using the Rothman-Greenland Method ([Rothman and Greenland, 1998](#)).

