#### 2.1.6 Treatment groups for analysis

Summaries will be presented according to the following combined treatment groups. If not mentioned otherwise, data from subjects discontinuing from the investigational product in studies D3461C00004 or D3461C00005, or who elect not to participate in the LTE, will be considered up to the adjusted analysis-defined visit window of Week 52 (ie, up to Day 378).

Primary:

- **Randomised Anifrolumab 300 mg:** Subjects randomised to anifrolumab 300 mg in studies D3461C00004 or D3461C00005 using all data from start of feeder study to end of LTE.
- **Randomised Placebo:** Subjects randomised to placebo in studies D3461C00004 or D3461C00005 using data from start of feeder study up until switch to anifrolumab 300 mg or to end of LTE for subjects re-randomised to placebo in LTE, respectively.

Supportive:

- **Placebo Feeder + Placebo LTE:** Subjects randomised to placebo in Studies D3461C00004 or D3461C00005 and re-randomised to placebo in LTE using all data from start of feeder study to end of LTE. Data from subjects not randomised into the LTE for any reason but that would have been re-randomised to placebo are included in this treatment group up to Week 52. Subjects who are not randomised into the LTE study will be assigned to Placebo or anifrolumab 300 mg via a

separate randomization process in order to determine who would have been re-randomised to placebo.

- **All Anifrolumab:** Subjects randomised to anifrolumab in studies D3461C00004 or D3461C00005, regardless of dose, and subjects randomised to placebo in studies D3461C00004 or D3461C00005 and then re-randomised to anifrolumab 300 mg in LTE, using all data from start of feeder study or switch to anifrolumab, respectively, to end of LTE. Baseline data from the feeder study will be included for all subjects.

Additional supportive:

- **Placebo Feeder + Anifrolumab 300 mg LTE:** Subjects randomised to placebo in studies D3461C00004 or D3461C00005 and then re-randomised to anifrolumab 300 mg in LTE using data from start of feeder study to end of LTE. Data from subjects not randomised into the LTE for any reason, but that would have been re-randomised to anifrolumab 300 mg are included in this treatment group up to Week 52. Subjects who are not randomised into the LTE study will be assigned to Placebo or anifrolumab 300 mg via a separate randomization process in order to determine who would have been re-randomised to anifrolumab 300 mg.

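### The pooled rates in the primary comparison mix study years differently (Year 1 expected at about 36% of anifrolumab and 59% of placebo person-time), and no planned output gives a time-adjusted contrast

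*SAP*

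**What the plan says.** SAP 4.2.1: "The primary assessment will be the comparison between the treatment groups" Randomised Anifrolumab 300 mg and Randomised Placebo.

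SAP 2.1.6 gives the two groups different data windows. The anifrolumab group contributes feeder and extension data throughout. The placebo group contributes "using data from start of feeder study up until switch to anifrolumab 300 mg or to end of LTE for subjects re-randomised to placebo". SAP 1.2 explains who leaves: "Subjects previously randomised to placebo will be re-randomised 1:1 to blinded anifrolumab 300 mg or placebo".

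SAP 3.1.1 defines the event rate as subjects with an event over summed exposure. An alternative rate stops the clock at the first event. Neither overall rate is stratified by time.

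The plan also provides time-specific material:
- AESI and SAE alternative rates by study year with 95% CIs (SAP 4.2.1.1)
- Kaplan-Meier plots for each AESI category (SAP 4.2.1.1)
- extension-only summaries, including summaries before and during the pandemic (SAP 4.2.1.1)
- a supportive Placebo Feeder + Placebo LTE group (SAP 2.1.6)
- an intention to explore rates over time (protocol 8.5.1)

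SAP 1.3 and protocol 8.2 state that no formal comparisons are planned and that each group gets its own estimate and CI.

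**The concern.** A pooled rate is an average of year-specific rates weighted by the person-time in each year. If two groups have different weights, their pooled rates differ whenever risk changes with time on study, even if the drug does nothing. Here the weights differ by design, because the placebo group loses half of its extension entrants at the switch.

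Events that cluster early would look less frequent on anifrolumab, and events that accumulate would look more frequent. This matters in a study whose purpose is long-term safety, and protocol 8.5.1 itself allows that risk may change with longer exposure. Unlike sampling error, this distortion does not shrink as events accrue.

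**Working it through.** **Inputs.** From SAP 1.3: "Assuming annual dropout rates of 30%, 30%, and 20% following placebo, anifrolumab 150 mg, and anifrolumab 300 mg"; "that 90% of the subjects completing studies D3461C00004 or D3461C00005 enter the LTE"; and "follow-up times of approximately 893, 517, and 1343 subject years" for Randomised Anifrolumab 300 mg, Randomised Placebo and All Anifrolumab. From SAP 1.2: the 1:1 re-randomisation, and "A 156-week treatment period with investigational product administered Q4W" (Years 2 to 4) after a 52-week feeder study (Year 1).

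**Assumptions.** The documents do not give the feeder sample sizes. I assume 360 (300 mg), 360 (placebo) and 90 (150 mg), found by solving back from the stated subject-years. I also assume dropout spread evenly within each year, and 20% annual dropout after any switch to 300 mg.

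**Reproducing the plan's figures.** Person-years per randomised subject:
- 300 mg: 0.90 + 0.8 × 0.9 × 0.90 × (1 + 0.8 + 0.64) = 2.481. Times 360 = 893.2.
- Placebo: 0.85 + 0.7 × 0.9 × 0.5 × 0.85 × (1 + 0.7 + 0.49) = 1.436. Times 360 = 517.1.
- All Anifrolumab: 893.2 + 201.0 (150 mg feeder) + 249.0 (placebo switchers) = 1343.2.

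These match 893, 517 and 1343. Exponential dropout gives 889.5, 511.7 and 1337.2.

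**Person-years by study year.**

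| | Year 1 | Year 2 | Year 3 | Year 4 |
|---|---|---|---|---|
| Randomised Anifrolumab 300 mg | 324.0 (36.3%) | 233.3 (26.1%) | 186.6 (20.9%) | 149.3 (16.7%) |
| Randomised Placebo | 306.0 (59.2%) | 96.4 (18.6%) | 67.5 (13.0%) | 47.2 (9.1%) |

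The shares do not depend on the assumed sample sizes and are the same under even or exponential dropout.

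**Where the gap comes from.** In the supportive Placebo Feeder + Placebo LTE group, which removes the effect of the switch, Year 1 is 42.0%. So 59.2 − 42.0 = 17.2 points of the gap come from the switch, and 42.0 − 36.3 = 5.7 points from the assumed difference in dropout.

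**Sensitivity.** With 300 mg dropout of 10-25%, placebo dropout of 20-35% and entry of 70-100%, the Year 1 share is 29-45% for anifrolumab and 51-68% for placebo. It is higher for placebo in every combination.

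**Crude ratio (300 mg / placebo) with no drug effect.** If the Year 1 rate is k times a constant later rate, and s is the Year 1 share, each pooled rate is proportional to 1 + s(k − 1).
- k = 2: 1.363 / 1.592 = 0.86. Against Placebo Feeder + Placebo LTE: 1.363 / 1.420 = 0.96.
- k = 1/2: 0.819 / 0.704 = 1.16.
- Rates rising 1, 1.5, 2, 2.5 over Years 1 to 4: 1.590 / 1.361 = 1.17.

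**Against sampling error**, for k = 2 (log ratio −0.155):
- At the plan's benchmark of 10 per 1000 subject-years, about 8.9 and 5.2 events are expected. The SE of the log ratio is √(1/8.93 + 1/5.17) = 0.55, so the distortion is about 0.28 SE.
- At 10 per 100 subject-years (my assumption, to represent a frequent outcome), 89.3 and 51.7 events are expected. The SE is 0.175, so the distortion is about 0.89 SE.

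**Cost of adjusting.** At equal rates, the SE of the rate difference relative to the crude SE is 1.026 with Mantel-Haenszel weights over the four years, and 1.034 when standardised to pooled person-time.

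**The case against.** The strongest reply is that the study disclaims formal comparisons, defines no rate ratio or difference, and already plans the outputs that expose the problem. By default the by-interval AESI and SAE tables show these two groups. The Kaplan-Meier plots share a time axis. The Placebo Feeder + Placebo LTE group is a standard column in the combined tables and brings the null ratio for a two-fold Year 1 risk from 0.86 to 0.96. No document says that any AESI's risk changes two-fold over time. For rare AESIs the distortion is lost in the noise.

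Most of this stands, and it settles the severity. It does not remove the point. SAP 4.2.1 still names a comparison as primary, and a descriptive contrast can mislead as a tested one can. Nothing combines the by-interval rates, and they are thin: at 10 per 1000, placebo Years 2, 3 and 4 each expect fewer than one event (0.96, 0.67 and 0.47). The Kaplan-Meier plots cover AESIs but not SAEs. The pandemic summaries use extension data only. The alternative event rate does not help: in simulation with a two-fold Year 1 risk its ratio is still about 0.86.

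A reader might go further and infer that the plan ignores time on study, or that the primary comparison is invalid. The list of planned outputs rules out the first. The moderate size, which depends on how risk actually changes, rules out the second.

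**Conclusion.** The point holds as a moderate weakness in how the primary comparison is summarised. The pooled AESI and SAE rates are confounded by time on study. With no drug effect, the expected ratio is about 0.86 or 1.16 when the Year 1 risk is double or half the later risk. This matters for frequent outcomes such as SAEs and little for rare AESIs.

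The 36% and 59% are expected shares from planning assumptions. They are not stated in the documents and are not observed data. The patterns of changing risk are illustrations. The model leaves out the follow-up to 84 days after the last dose that SAP 3.1.1 counts as exposure, although the plan's own totals reproduce without it.

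It would also be tempting to read this as confounding by calendar time that stratification by study year would cure. The documents do not support that. Study year stands in for calendar time only as far as the arms were enrolled in parallel.

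**What to change.** In SAP 4.2.1, base the primary descriptive comparison on AESI and SAE rates combined over all time intervals of SAP 3.1.1. Either standardise each group's rate directly to the pooled person-time, which keeps the per-group format, or report a Mantel-Haenszel rate difference. Give 95% CIs and no hypothesis test, and keep the crude rates as supportive. Name the CI method, because the exact Poisson limits planned in SAP 4.1.3 do not carry over directly to a weighted rate.

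Include the interval after Year 4, merged with Year 4 if sparse. For completers it holds about 8 weeks: last dose at LTE Week 152 (1064 days) plus 84 days is 1148, and the interval starts at 1092. Stopping at Year 4 would drop those events.

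Add two sentences on limits. The adjustment does not correct for differential dropout before the extension, since Years 2 to 4 compare entrants retained at different assumed rates. It addresses calendar time only as far as enrolment was parallel.

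The cost is SAP wording, one table built from interval rates already planned, and a standard error of the difference about 3% larger at equal rates. This is a worthwhile improvement, not a condition for proceeding.
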